### 9.4.4.2 Safety

#### **Safety Population:**

The safety population will include all non-censored subjects who received the Restoration® ADM Acetabular Shell and Restoration® ADM X3® Acetabular Insert.

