### 9.4.4 Efficacy Patient Populations

### 9.4.4.1 **Efficacy**

#### Per protocol population:

The study population for analysis will include all subjects who receive the Restoration® ADM Acetabular Shell and Restoration® ADM X3® Acetabular Insert and have the primary efficacy variable measurements available. This does not include cases censored from analysis for a reason that may have a significant impact on outcome.

The primary efficacy analysis will be based on the per protocol population.

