### 9.4.4.3 Survival Analysis

#### **Modified intent to treat population:**

Subjects enrolled in the study who received the Restoration® ADM Acetabular Shell and Restoration® ADM X3® Acetabular Insert will be included in the survival analysis.

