# 10.3 Early Withdrawal of Subjects

### When and How to Withdraw Subjects

In the event that the subject is discontinued by the investigative center prior to the final study evaluation, the subject will be notified by the center that he/she is no longer in the study and a Study Termination eCRF will be completed.

The following is a list of reasons for which subjects may be withdrawn and the date of termination that should be used on the Study Termination eCRF in each situation. This list is not all inclusive:

Termination Reason	Date of Termination
Death	Date of death
Investigative center termination	Date of study close-out visit
Lost to follow-up	Date Stryker termination approval given
Voluntary withdrawal	Date subject notified center of withdrawal
Revision/removal of study device	Date of revision/removal procedure
Study device not implanted	Date of surgery
Surgery not performed	Date Stryker termination approval given

At the time of study surgery it is required that the following components are implanted for each treatment group:

Restoration® ADM X3® System with any compatible Stryker Stem:

- Restoration® ADM Acetabular Shell
- Restoration® ADM X3® Acetabular Insert

- o 28 mm Stryker femoral head (except for the LFIT™ Anatomic CoCr femoral bearing head)
- Compatible Stryker femoral stem (with a minimum of 100 Accolade® II Hip Stems)

Revision or removal of the Restoration® ADM X3® Acetabular System (acetabular shell and insert) constitutes a failure and study termination for the subject.

If femoral stem or femoral head revision is required during the study, the event is considered a reoperation and does not constitute a failure or study termination.

If the subject fails to return for his/her follow-up appointments, every effort should be made to contact the subject to assess his/her health status. If, after attempting to contact the subject through three documented phone calls and a certified letter, the subject still does not respond, he/she will be considered lost to follow-up. A Study Termination eCRF will be completed only after notifying Stryker of the subject's status and being given approval to terminate.

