Intraoperative fissure, fracture, or perforation of the femur, acetabulum or trochanter can occur due to impaction of the component into the prepared femoral canal or acetabulum. Postoperative femoral or acetabular fracture can occur due to trauma, the presence of defects or poor bone stock.

Metal sensitivity reactions have been reported following joint replacement.

AEs may necessitate reoperation, revision, arthrodesis of the involved joint, girdlestone or amputation of the limb.

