# 12.3 Expected Complications and Rates of Occurrences

Complications associated with THA procedures, such as those performed with the Restoration® ADM X3® Acetabular System, have been reported. These include the potential for: injury to the hip's neurovascular structures, loosening of the components, malseating of the acetabular liner, heterotopic bone formation, infection, deep vein thrombosis, pulmonary embolism, metal sensitivity reactions, intraoperative or postoperative fracture of the femur or acetabulum, and the need for re-operation, revision, arthrodesis of the involved joint, girdlestone or amputation of the limb. The safety objective will compare the complication rates of the Restoration® ADM X3® Acetabular System to published rates.

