### **SURGICAL DETAILS**

| GENERAL INFORMATION                                                                 |                                                                        |                                         |
|-------------------------------------------------------------------------------------|------------------------------------------------------------------------|-----------------------------------------|
| SUBJECT INITIALS:                                                                   | SURGERY DATE:  (DD-MMM-YYYY)  RF only if surgery is performed and subj | SUBJECT ID:  ect receives study device. |
| I. SURGICAL DETAILS                                                                 | ar only it surgery is performed and susj                               | ect receives study device.              |
| A. APPROACH Anterior/ Anterolateral Posterior/ Posterolateral Dual Incision Lateral |                                                                        | QUIRED?  C. NAVIGATION USED?  Yes  No   |
| D. INCISION LENGTH E. DURA                                                          | TION OF SURGERY                                                        | F. ESTIMATED BLOOD LOSS                 |
| cm Skin to                                                                          |                                                                        | сс                                      |
| II. PROSTHESIS                                                                      |                                                                        |                                         |
| G. PROSTHESES -                                                                     | H. OTHER?                                                              |                                         |
| Upload a PDF copy of the component label(s) in                                      | nplanted. *If Yes, specify                                             | and attach a copy of the label(s):      |
| Please go to Subject Information screen and en in Products tab.                     | Reset                                                                  | her (Specify) Reference # Lot #         |
| Acetabular Shell                                                                    | X                                                                      |                                         |

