|            | List efforts to                                                       | 1st phone call:                                             |                            | (DD-MMM-YYYY)                   |       |  |  |
|            | contact subject:                                                      | 2nd phone call:                                             |                            | (DD-MMM-YYYY)                   |       |  |  |
|            |                                                                       | 3rd phone call:                                             |                            | (DD-MMM-YYYY)                   |       |  |  |
|            |                                                                       | Certified letter sent                                       |                            | (DD-MMM-YYYY)                   |       |  |  |
|            | Additional efforts:                                                   |                                                             |                            |                                 |       |  |  |
| $\bigcirc$ |                                                                       | Study Device (Complete vision / removal procedure           |                            | e.                              |       |  |  |
| $\bigcirc$ | Study Device Not im                                                   | olanted (Specify below) urgery as the Termination D         | ate.                       |                                 |       |  |  |
| $\bigcirc$ |                                                                       | Select if subject voluntarily ect notified site of withdraw |                            |                                 |       |  |  |
| $\bigcirc$ | Surgery Not Perform
Enter date of su                               | ed (Specify below) urgeon termination or surge              | ery cancellation as the Te | ermination Date.                |       |  |  |
| 0          | Other (Specify below)                                                 |                                                             |                            |                                 |       |  |  |
|            |                                                                       |                                                             |                            |                                 |       |  |  |

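### Intraoperative complications that make the surgeon abandon the ADM shell fall outside the only defined safety denominator, and no conversion rate is planned

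*Combined protocol and SAP*

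**What the plan says.** All three analysis populations depend on receipt of both components.

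- Safety (section 9.4.4.2): "The safety population will include all non-censored subjects who received the Restoration® ADM Acetabular Shell and Restoration® ADM X3® Acetabular Insert".
- Per protocol (section 9.4.4.1): "The study population for analysis will include all subjects who receive the Restoration® ADM Acetabular Shell and Restoration® ADM X3® Acetabular Insert", with further conditions.
- Modified intent to treat, for survival (section 9.4.4.3): "Subjects enrolled in the study who received the Restoration® ADM Acetabular Shell and Restoration® ADM X3® Acetabular Insert".

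Section 10.3 lists "Study device not implanted" as a reason for termination, dated at the day of surgery. It is a separate row from surgery that was not performed, so the plan foresees subjects who are operated on and leave without the device. In Appendix F, the Surgical Details form is to be completed "only if surgery is performed and subj" (the line is broken in the extracted text; it goes on to require that the subject receives the study device). That form holds the yes/no item on intraoperative complications.

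Section 12.3 states: "The safety objective will compare the complication rates of the Restoration® ADM X3® Acetabular System to published rates". Its list of complications includes intraoperative fracture of the femur or acetabulum, and section 12.2 gives a mechanism: "Intraoperative fissure, fracture, or perforation of the femur, acetabulum or trochanter can occur due to impaction of the component". Under section 3.3, enrolment runs until 350 cases have received the system.

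**The concern.** Take a consented subject in whom the shell is impacted, the acetabulum fractures or the shell does not hold, and another cup is used. This subject is terminated that day, has no Surgical Details form, belongs to none of the three populations, and does not count towards the 350. The complication is one that section 12 names and intends to compare with published rates.

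A recipients-only rate is conditional on successful implantation. The events it leaves out are those severe enough to end the attempt. Failure to implant a press-fit shell is also an outcome of using it, and the plan defines no rate for it. What is at stake is the completeness of a descriptive safety comparison, not the primary endpoint.

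**Working it through.** **The plan's own figures.** The plan gives no figure for failed attempts or intraoperative complications. Its sample size can be reproduced, to show that this point leaves it alone. The inputs from section 9.4.2 are a 97% success rate, a 93.5% threshold and one-sided 5% error. Power is not stated; 80% is assumed here.

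- n = (1.645·√(0.935·0.065) + 0.842·√(0.97·0.03))² / 0.035² = 246.1.
- With continuity correction: (246.1/4)·(1 + √(1 + 2/(246.1·0.035)))² = 273.9, so 274.
- Allowing for 20% loss: 274/0.8 = 342.5, so 343; 350 are enrolled.

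None of these depends on how attempts without implantation are counted.

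**Where such a subject can be recorded**

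| Place | Covers an attempt without implantation? |
|---|---|
| Populations, 9.4.4.1 to 9.4.4.3 | No: both components must be received |
| Surgical Details form | No: recipients only |
| Adverse event form | Yes: reporting starts at consent (8.1), and the form has an intraoperative option |
| Deviation form and 11.6 | Yes: non-implantation is a listed deviation, and the form asks why it occurred |
| Termination form | Yes, with a field to specify; attempted and never attempted are not told apart |
| 9.4.4.4 | Possibly: deviations that could affect outcome are removed from the efficacy and safety populations and reported separately |
| 9.2.2 | Unclear: reported adverse events are tabulated with percentages, but no population is named |

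The data can exist. What is missing is a defined rate that includes them.

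**Size.** Let r be the complication rate among the 350 recipients, f the share of all attempts that fail, and q the share of failed attempts with a complication. Then k = 350·f/(1 − f), and

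all-attempts rate = (350·r + k·q) / (350 + k).

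This exceeds r whenever k > 0 and q > r. The documents give none of r, f or q, so all values are assumptions: f from 1% to 5%, q from 25% to 100%, r from 1% to 3%.

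- f = 1%: k = 350·0.01/0.99 = 3.5, rounded to 4.
- f = 5%: k = 350·0.05/0.95 = 18.4, rounded to 18.
- r = 2%, low end: (7 + 4·0.25)/354 = 8/354 = 2.26%, or 1.13 times r.
- r = 2%, high end: (7 + 18)/368 = 25/368 = 6.79%, or 3.40 times r.

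| Rate among recipients | k = 4, q = 25% | k = 18, q = 100% |
|---|---|---|
| 1% | 1.27% | 5.84% |
| 2% | 2.26% | 6.79% |
| 3% | 3.25% | 7.74% |

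With k = 0 the two rates are equal.

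**What a conversion rate would show.** Exact 95% intervals over all attempts are 0/350 = 0% (0 to 1.05%), 4/354 = 1.13% (0.31% to 2.87%) and 18/368 = 4.89% (2.92% to 7.62%). Even zero conversions would be informative.

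**The case against.** Four arguments weigh on the other side.

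1. **Failed implantation is not invisible.** It reaches the deviation and termination forms with a reason, the adverse event form has its own intraoperative option, and section 9.4.4.4 offers separate reporting. The limit on Surgical Details appears only in the form specifications, which section 11.1 calls draft; section 7.2 has no such limit. This stands. A reader might infer that these events are lost or reported nowhere, and the documents do not support that. But none of these routes puts the events into a defined rate.

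2. **Section 9.2.2 may already include them.** It covers adverse events without naming a population. That is fair as far as it goes, but the only safety denominator defined is the one in section 9.4.4.2. A numerator from all reports over a recipients-only denominator would be a mismatch of its own.

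3. **Bias against the literature is not shown.** Published series may also count recipients only. Section 1.1 describes a dual-mobility series and an X3 insert study in those terms. If the safety comparators are built that way, the present population is like for like. This stands. A reader might infer that the comparison is biased in the device's favour, but that depends on comparator denominators which the documents do not give.

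4. **Conversions may be rare.** Section 3.4 requires five cases at a centre before enrolment. The plan never describes a switch of cup, and the termination category may include shells that were never attempted. This is also fair, and is why the size is given as a range starting from no effect.

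**Conclusion.** The gap is real and narrow. Attempts that end without the device lie outside the only defined safety denominator. The routine prompt for intraoperative complications is not required for them, and no conversion rate is planned. Complications in subjects who do receive shell and insert are captured.

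Under the assumed ranges, a 2% recipients-only rate corresponds to about 2.3% to 6.8% over all attempts, or 1.13 to 3.4 times as high; with no failed attempts nothing changes. These figures hold only if the same complication definition is used in both rates. Setting fractures among recipients against fractures plus fixation failures over all attempts would exaggerate the contrast.

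A reader might also infer that the whole safety population should be redefined by attempt. That would place subjects without the device, terminated on the day of surgery, in the denominators for psoas impingement, groin pain and revision, and would dilute those rates. Section 9.4.4.4 could also censor them again. A separate set avoids both problems. The change should be made, but the primary endpoint does not depend on it.

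**What to change.** 1. Keep the safety population of section 9.4.4.2 for postoperative rates: psoas impingement, groin pain, radiographic stability, and revision or removal.
2. Add to sections 9.2.2 and 9.4.4.2 an implantation-attempted set: all consented subjects in whom implantation of the ADM shell was attempted, whether or not it was retained. State what counts as an attempt, and exempt the set from censoring under section 9.4.4.4 for non-implantation.
3. Over that set, report intraoperative complications and conversions with reasons, with 95% intervals, next to the recipients-only rate so that either can be matched to the literature denominator.
4. Name the denominator of each rate in section 9.2.2.
5. Have sites complete the intraoperative items of Surgical Details for every attempt, and split the not-implanted reason on the termination form into attempted and not attempted.

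The cost is a few sentences, one form instruction, one tick box and one extra table, with a slightly less favourable intraoperative rate if conversions occur. The figures 274, 343 and 350 and the efficacy populations stay as they are.

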### 9.4.4.3 Survival Analysis

#### **Modified intent to treat population:**

Subjects enrolled in the study who received the Restoration® ADM Acetabular Shell and Restoration® ADM X3® Acetabular Insert will be included in the survival analysis.

### 9.4.4.4 Censored Cases

In the event that a protocol deviation occurs which could affect subject outcome, the data for the affected subject will be censored from the Efficacy and Safety Subejct Populations. All cases that fall into this category will be reported separately.

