# 2.2 Safety

All operative site events as well as all serious adverse events (SAEs), excluding elective procedures, will be collected and compared to published data. It is expected that the AE rates reported for the Restoration® ADM X3® Acetabular System will be comparable to those reported in the literature for other primary THR systems and similar dual mobility cups on the market. Details regarding AE definitions, recording and reporting are in Section 8 of this protocol, Adverse Events.

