# 9.2 Safety Parameters

# 9.2.1 Safety Parameters

Safety parameters will include

- All AEs reported
- Rate of psoas impingement
- Rate of associated groin pain (derived from the 'Operative Site Other' field on the AE form)

- Radiographic stability at each postoperative visit
- Revision or removal of any study component
- Revision or removal of the Restoration® ADM Acetabular Shell and X3®
   Acetabular Insert

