### 9.2.2 Safety Analysis

All AEs will be listed, tabulated and summarized by event, number and percent of cases/subjects. AE rates and 95% confidence intervals will be presented.

For categorical variables, such as radiographic stability, the number and percent in each category will be presented.

The Kaplan-Meier survival curve of revision/removal of any study component and the Restoration® ADM Acetabular Shell and X3® Acetabular Insert will also be displayed.

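### The safety population leaves out implanted subjects who had an outcome-relevant protocol deviation, so the pooled AE rates set against the literature would omit exposed patients

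*Combined protocol and SAP*

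**What the plan says.** All references are to the combined protocol and SAP.

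- **Safety set.** Section 9.4.4.2: "The safety population will include all non-censored subjects who received" the study shell and insert. Receiving the device is necessary but not sufficient.
- **Who is censored.** Section 9.4.4.4 applies to any subject with a deviation that could influence outcome: "the data for the affected subject will be censored from the Efficacy and Safety Subejct Populations". It adds: "All cases that fall into this category will be reported separately".
- **What the safety data are for.** Section 2.2: "All operative site events as well as all serious adverse events (SAEs), excluding elective procedures, will be collected and compared to published data". Section 12.3 repeats that complication rates will be compared with published rates.
- **What is calculated.** Section 9.2.2: "AE rates and 95% confidence intervals will be presented". It names no analysis population. The parameters in 9.2.1 include "Rate of psoas impingement", associated groin pain and radiographic stability.
- **Survival set.** Under 9.4.4.3, enrolled subjects who received the shell and insert "will be included in the survival analysis". There is no exclusion for deviations.

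**The concern.** A safety rate should describe everyone exposed to the device. Here a patient can carry the shell and insert for ten years and still be left out of the numerator and denominator of the pooled AE rate. The trigger is that the deviation might influence outcome, so those removed may well differ in AE risk from those kept.

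The study has no control arm. A published rate is the only yardstick, and nothing in a comparator group offsets a selective denominator. At stake are the AE rates and intervals that a reader would set beside the literature, including those for psoas impingement and groin pain, which the anatomic cut-out of the shell is meant to reduce.

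**Working it through.** **1. Is the exclusion the plan's rule or a slip in one place?** Sections 9.4.4.2 and 9.4.4.4 say the same thing independently: one limits the safety set to subjects who were not censored, and the other names the safety population as one from which they are censored. It is the rule.

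**2. Can it reach implanted subjects?** Section 11.6 lists deviations. Two can plainly occur with shell and insert in place and could bear on outcome: enrolment against the eligibility criteria, and a specified component not used (a head or stem, for example). Many of the others concern visits, such as late or missed visits and unreadable films. Cases without the shell or insert fall outside every set and are not at issue.

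**3. Which outputs are affected?**

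| Output | Population | Deviation cases kept? |
|---|---|---|
| Dislocation curve (9.1.4) | Survival set, 9.4.4.3 | Yes |
| Revision/removal curves (9.2.2) | Survival set, 9.4.4.3 | Yes |
| AE rates and 95% intervals (9.2.2) | Not named; 9.4.4.2 is the only safety set | No, on that set |
| Psoas impingement, groin pain, radiographic stability (9.2.1) | As above | No, on that set |

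**4. Which way could a rate move?** Let *k* be the fraction of implanted cases censored, *r* the AE rate in those kept, and *R* the AE risk of censored relative to kept cases. Then

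all-implanted rate = (1 − *k*)·*r* + *k*·*R*·*r* = *r*·[1 + *k*(*R* − 1)].

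If *R* = 1 there is no bias, only a smaller denominator. If *R* > 1 the planned rate is too low; if *R* < 1 it is too high. The documents fix neither *k* nor *R*.

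**5. How large might it be?** The plan gives no figure to reproduce on this point. Its only usable input is 350 implanted cases (3.3, 9.4.2). *Assumed:* 18 cases (18/350 = 5.1%) or 35 cases (10%) censored, with *R* from 1 to 3.

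- 18 censored, *R* = 3: 1 + (18/350)·2 = 1.10.
- 35 censored, *R* = 3: 1 + 0.10·2 = 1.20, so the planned rate is 1/1.20 = 0.83 of the all-implanted rate, about 17% too low in relative terms.

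With whole counts, exact (Clopper-Pearson) 95% intervals, and an assumed 35 events among the 350:

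| Cases censored | Events among them | Rate reported | 95% CI |
|---|---|---|---|
| 0 | – | 35/350 = 10.0% | 7.1-13.6% |
| 18 | 0 | 35/332 = 10.5% | 7.5-14.4% |
| 18 | 2 | 33/332 = 9.9% | 6.9-13.7% |
| 18 | 4 | 31/332 = 9.3% | 6.4-13.0% |
| 35 | 0 | 35/315 = 11.1% | 7.9-15.1% |
| 35 | 7 | 28/315 = 8.9% | 6.0-12.6% |

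For a rarer event, an assumed 7/350 = 2.0% becomes 7/332 = 2.1% if none of the 7 is among the 18 censored, or 4/332 = 1.2% if three are.

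**The case against.** The case against has several good parts.

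- **The events are disclosed.** Section 9.4.4.4 requires separate reporting of censored cases, and a reader could rebuild the full rate if that report gives counts by event. This stands, and it limits the harm. It does not put those patients into the rate or interval that the plan presents.
- **The link to the AE rates is inferred.** Section 9.2.2 begins with all AEs and names no population. The synopsis speaks of AE rates for the acetabular system group, which could mean everyone who received it. This stands as a caveat. However, no section plans AE rates on all implanted subjects, and 9.4.4.2 is the only safety set defined.
- **The number affected may be small.** Many listed deviations concern visits, and the 5-10% used above has no basis in the documents. This also stands. Every shifted point estimate in the 10% example lies inside the uncensored interval of 7.1-13.6%.

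A reader might infer more than the documents support in three ways:

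- *That complications are being concealed.* Separate reporting and the unrestricted survival set contradict this.
- *That AE rates will look too favourable.* Direction depends on who is censored, and the rate can equally come out too high.
- *That the primary result is compromised in the same way.* The per-protocol definition in 9.4.4.1 does carry a similar exclusion ("This does not include cases censored from analysis for a reason that may have a significant impact on outcome"). A per-protocol set is a recognised choice for non-inferiority, though, and exclusions unrelated to dislocation do not bias the success rate. A false-positive problem would need dislocators to be excluded more often than others, and nothing in the documents indicates that.

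**Conclusion.** The point holds for the safety population. As written, the pooled AE rates and 95% intervals would leave out exposed patients. This rests on one reasonable inference: that 9.2.2 uses the population 9.4.4.2 defines.

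The size and direction of any bias cannot be determined from the documents. Under the assumptions shown, a 10.0% rate is reported as anything from 8.9% to 11.1%. The shifts are modest in absolute terms but can be larger in relative terms for a rare event. There is no safety hypothesis or threshold, so no test can change its result. The definition should still be corrected, because the denominator is wrong for its stated purpose and the correction needs no new data.

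**What to change.** 1. In 9.4.4.2, delete the word *non-censored*, so that the safety population is every subject who received the shell and insert.
2. In 9.4.4.4, delete *and Safety*, so that deviation censoring applies to the efficacy population only.
3. In 9.2.2, name this all-implanted set as the population for AE rates and their 95% intervals.
4. Keep the separate listing of deviation cases.

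**Cost.** Two deletions and one phrase, using data already collected. Some reported AE rates may look slightly less favourable.

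**Optional, lower priority and separate from this point.** Beside the per-protocol primary result, show the 10-year dislocation success rate with its lower bound on all implanted cases, as a sensitivity analysis without a second pass rule.
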